8.8 NON-EVALUABLE

In a patient who does not have evidence of PD, the occurrence of any of the following conditions indicates a response status of NE:

- There are no images or inadequate or missing images
- Images of the liver and spleen are missing at that time point (with the exception that absence of splenic images will not result in an NE designation in a patient known to have undergone splenectomy).

Note: A time-point will be considered to have a response of NE if any target lesion is missing. PD may be assigned at any time point regardless of the extent of missing target or non-target lesions. Missing non-target lesions will not impact the ability to assess for response or disease progression.

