8.2 IDENTIFICATION AND MEASUREMENT OF TUMOR LESIONS AND ORGANOMEGLALY

8.2.1 TARGET LESIONS

For patients with measurable adenopathy/disease at baseline, up to 6 lymph nodes should be selected as target lesions that will be used to quantitate the status of the disease during study treatment. Ideally, the target lesions should be located in disparate regions of the body. Only peripheral nodes need be selected as target lesions. However, it is optimal if mediastinal and retroperitoneal areas of disease are assessed whenever these sites are involved.

Target lesions will be measured and recorded at baseline and as per the study assessment schedule. The cross-sectional dimensions (the largest cross-sectional diameter, i.e., the LD x LPD) will be recorded (in cm) for each target lesion. The product of the perpendicular diameters (PPD) (in cm²) for each target

lesion and the sum of the products (SPD) (in cm^2) for all target lesions will be calculated and recorded. The baseline SPD will be used as references by which objective tumor response will be characterized during treatment. The nadir LD of individual lesions and the nadir SPD will be used as references by which CLL progression will be characterized. All LD and LPD diameters will be reported in centimeters and all PPDs and SPDs will be reported in centimeters squared.

A nodal mass may be selected as a nodal target lesion if it is both abnormal and measurable at baseline. A lymph node lesion is considered abnormal if it has a single diameter that is $> 1.5 \text{ cm}$ and is considered measurable if it has 2 perpendicular diameters that can be accurately measured in cross section with the LD being $\geq 1.0 \text{ cm}$ and the LPD also being $\geq 1.0 \text{ cm}$.

At follow-up time points, the LDs for individual lesions and the SPD of all nodal target lesions will be considered. Because nodal target lesions that have one or both diameters $> 0 \text{ cm}$ and $< 1.0 \text{ cm}$ cannot be reliably measured, a default value of 1.0 cm will be assigned for each diameter that meets these criteria and the resulting PPD will be used in SPD calculations. Based on this convention, a CR may be achieved even if an SPD value is $> 0 \text{ cm}^2$ (i.e., if all lymph nodes measure $< 1.0 \text{ cm}^2$).

A new node that measures $> 1.5 \text{ cm}$ in the LD and $> 1.0 \text{ cm}$ in the LPD will be considered progressive disease.

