8.2.3 NON-TARGET LESIONS

Any other measurable and abnormal nodal lesions not selected for quantitation as target lesions may be considered non-target lesions. In addition, non-measurable evidence of CLL such as nodal lesions with both diameters $< 1.0 \text{ cm}$, extra-nodal lesions, bone lesions, leptomeningeal disease, ascites, pleural or pericardial effusions, lymphangitis of the skin or lung, abdominal masses that are not confirmed and followed by imaging techniques, cystic lesions, previously irradiated lesions, and lesions with artifacts may be considered as non-target disease.

The presence or absence of non-target disease should be recorded at baseline and at the stipulated intervals during treatment. If present at baseline, up to 6 non-target lesions should be recorded. The non-target disease at baseline will be used as a general reference to further characterize regression or

progression of CLL during assessments of the objective tumor response during treatment. Measurements are not required and these lesions should be followed as “present” or “absent”.

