8.4 COMPLETE RESPONSE

To satisfy criteria for a CR, all of the following criteria must be met:

- No evidence of new disease
- ALC in peripheral blood of $<4 \times 10^9/L$
- Regression of all target nodal masses to normal size ≤ 1.5 cm in the LD
- Normal spleen and liver size
- Regression to normal of all nodal non-target disease and disappearance of all detectable non-nodal, non-target disease
- Morphologically negative bone marrow defined as $<30\%$ of nucleated cells being lymphoid cells and no lymphoid nodules in a bone marrow sample (the presence of benign reactive nodules is still compatible with a CR)
- Absence of constitutional symptoms
- Peripheral blood counts meeting all of the following criteria:
 - ANC $>1.5 \times 10^9/L$ without need for exogenous growth factors (e.g., G-CSF)
 - Platelet count $\geq 100 \times 10^9/L$ without need for exogenous growth factors
 - Hemoglobin $\geq 110 \text{ g/L}$ (11.0 g/dL) without red blood cell transfusions or need for exogenous growth factors (e.g., erythropoietin)

Patients who fulfill all the criteria for a CR (including bone marrow criteria) but who have a persistent anemia, thrombocytopenia, or neutropenia or a hypocellular bone marrow that is related to prior or ongoing drug toxicity (and not to progressive CLL) will be considered as a CR with incomplete marrow recovery (CRI). These patients remain eligible for MRD assessments and will discontinue therapy if negative for residual disease (similar to management for patient achieving a CR)

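### Sections 8.4 and 8.8 conflict on whether CR or CRi can be assigned when baseline non-target disease was not assessed; the exposure is narrow, but any error raises the primary endpoint

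*Combined protocol and SAP*

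**What the plan says.** Section 8.4 is conjunctive: "To satisfy criteria for a CR, all of the following criteria must be met". One of the listed criteria is "Regression to normal of all nodal non-target disease and disappearance of all detectable non-nodal, non-target disease". CRi carries the same requirement, apart from persistent cytopenia or a hypocellular marrow due to drug toxicity.

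Section 8.8 defines when a time point is non-evaluable. Its first bullet is "There are no images or inadequate or missing images", and its second covers missing liver and spleen images. A note then treats the two kinds of lesion differently. For target lesions, "A time-point will be considered to have a response of NE if any target lesion is missing". PD may be called whatever is missing. For non-target lesions, "Missing non-target lesions will not impact the ability to assess for response or disease progression".

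Section 8.2.1 caps the targets: "up to 6 lymph nodes should be selected as target lesions". It requires only peripheral nodes to be chosen and calls assessment of involved mediastinal and retroperitoneal sites optimal. Under Section 8.2.3, "Any other measurable and abnormal nodal lesions not selected for quantitation as target lesions may be considered non-target lesions", and extra-nodal lesions, bone lesions, leptomeningeal disease and effusions may also be non-target. The same section asks for follow-up: "The presence or absence of non-target disease should be recorded at baseline and at the stipulated intervals during treatment". It gives no consequence if this is not done.

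Section 9.6 counts CR and CRi as successes among treated patients. It makes a patient a non-responder when there is no tumor response assessment, and is silent on an assessment that is only partly complete.

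**The concern.** CR is one of the response categories in Section 8.3, so a statement about the ability to assess response covers CR unless it says otherwise. The sentence just before it in the 8.8 note already frees PD from any dependence on missing lesions. What the disputed sentence adds is therefore response, and that is the part that meets the 8.4 criterion head on. Two assessors could read the same incomplete data and reach different answers, each with a section to cite.

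This matters because the CR rate is the primary endpoint of a single-arm estimation study, with no comparator in which the same leniency would operate. CR or CRi status also feeds the MRD-based discontinuation criterion in Sections 4.1 and 4.3, so an ambiguity in CR carries over to that criterion. Those passages need to be reconciled with 8.4 and 8.8.

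**Working it through.** **1. The plan's own precision figures.** Inputs from Section 9.1: n = 40, anticipated CR rate 20% (x = 8), exact two-sided 95% interval. The Clopper-Pearson limits are

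- lower = the 0.025 quantile of Beta(x, n − x + 1)
- upper = the 0.975 quantile of Beta(x + 1, n − x)

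For 8/40 these give 9.05% to 35.65%, width 26.60%. The widest interval is at 20/40: 33.80% to 66.20%, width 32.40%. Both agree with the stated 9.1% to 35.6% (width 26.6%) and maximum of 32.4%, apart from rounding.

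**2. Where the two sections give different answers.** Take a patient who meets every other CR criterion and had non-target disease at baseline.

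- *A required body region was not scanned, or the images are inadequate.* The first NE bullet of 8.8 applies, and the second also applies if liver and spleen images are missing. The time point is NE, not CR.
- *All regions were adequately imaged and the non-target site is visible.* The assessor can see whether it persists, so nothing is missing and 8.4 decides.
- *The site lies outside the scheduled CT field or is not resolved by the images, or its status was not recorded.* No NE bullet clearly applies. Under 8.4 CR is not shown. Under the 8.8 note, response can be assessed regardless. This is the conflict.
- *The CT was waived.* Footnote 6 of Table 5.1 drops the cycle 12 and 24 scans when there is no measurable disease at baseline. Section 8.2.3 lists extra-nodal lesions and effusions among non-measurable disease, so such a patient can have baseline non-target disease and no follow-up scan by design. The first NE bullet, taken literally, makes the time point NE. If a waived scan is not regarded as missing, the 8.8 note allows CR. The text does not settle which.

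**3. Direction.** Every CR under a strict reading of 8.4 is also a CR under the literal reading of 8.8, but not the reverse. The difference in CR count is therefore zero or positive.

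**4. Size per patient.** 1/40 = 2.5 percentage points, assuming all 40 are treated. The number affected, k, is not in the documents. The values below are illustrative assumptions, starting from the anticipated 8/40:

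| k | CR rate | Exact 95% interval |
|---|---|---|
| 0 | 8/40 = 20.0% | 9.05% to 35.65% |
| 1 | 9/40 = 22.5% | 10.84% to 38.45% |
| 2 | 10/40 = 25.0% | 12.69% to 41.20% |

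**The case against.** The best defence is that being evaluable is not the same as qualifying. The sentence sits in the section on non-evaluable time points and says only that assessment remains possible; it does not say the non-target criterion is waived or deemed met. Read together with 8.4, the time point stays evaluable, PR, SD or PD may be assigned, and CR is simply not shown. That reading is sensible and probably what a careful assessor would do. It is not written down, however, and nothing makes 8.4 prevail over an unqualified statement about response.

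A reader might go further and infer that a patient whose chest or retroperitoneum was not imaged at cycle 12 would be counted as a CR. The documents do not support that. Table 5.1 schedules CT of neck, chest, abdomen and pelvis, so an unscanned region means missing images, and the NE bullets largely catch it. Nor does the freedom to choose only peripheral targets mean deep disease goes unassessed: 8.2.1 encourages assessment of those sites and 8.2.3 asks for non-target status at each interval.

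It is also fair that a CR still needs normal target nodes, spleen and liver, acceptable counts, no constitutional symptoms and a negative marrow, and that the MRD-based criterion additionally requires undetectable MRD. These conditions narrow the route to an unsupported CR without closing it. The point that the shift is small against an interval 26.6 points wide, in a study with no success threshold, also stands. It limits the importance of the issue but does not remove the contradiction.

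**Conclusion.** The conflict is real, and it concerns the primary endpoint. It reaches a small set of cases: non-target disease outside or not resolved by the available images, not recorded, or not re-imaged. Within that set each patient is worth 2.5 points of the CR rate, always upward relative to 8.4, if 8.8 is taken literally; if assessors apply 8.4 strictly, the effect is nil. A reader might infer that the plan as written inflates the CR rate by some definite amount. It does not show that: the documents give no count of affected patients, and the one- and two-patient rows above are illustrations, not estimates. The planned sample size and precision are unaffected. The point is worth correcting because the answer for the primary endpoint should not depend on which section an assessor reads.

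**What to change.** Amend the non-target sentence in Section 8.8 to this effect: missing non-target lesions do not by themselves make a time point NE and do not prevent PR, SD or PD. For the CR-rate endpoint, CR or CRi is assigned only if all non-target disease recorded at baseline was assessed at that time point and meets Section 8.4. Otherwise the time point takes the best non-CR category whose criteria are met, or NE where the image bullets of 8.8 apply. The last clause is needed because an automatic PR would contradict those bullets.

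In the same edit, state whether a CT waived under footnote 6 of Table 5.1 counts as a missing image, and cross-refer from Section 9.6 so that partly complete assessments are covered. Sections 4.1 and 4.3 should be reconciled with the result, since they use CR status.

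The cost is one amended sentence and these short clarifications. No sample size, visit or analysis method changes. The downside is that an occasional patient with incomplete data, who may truly be in CR, is not counted as one.

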8.9 LYMPHOCYTOSIS DURING THERAPY

Upon initiation of acalabrutinib, a temporary increase in lymphocyte counts (i.e., $\geq 50\%$ increase from baseline and above absolute lymphocyte count of 5,000/mcL) may occur. The onset of isolated lymphocytosis usually occurs during the first few weeks of acalabrutinib therapy. Patients with lymphocytosis should be continued on study drug until the occurrence of definitive disease progression

(i.e., disease progression that is manifest by worsening CLL-related signs other than lymphocytosis alone), or the occurrence of another reason to discontinue study therapy. Unless related to treatment interruption, new or increasing lymphocytosis after 6 months of starting treatment may be considered disease progression and should be confirmed as per the response criteria.

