4 STUDY DESIGN

4.1 OVERVIEW OF STUDY DESIGN

This is an open label, Phase II trial of acalabrutinib and high frequency low dose subcutaneous rituximab in previously untreated CLL patients requiring therapy. Subjects will be recruited from the James P. Wilmot Cancer Center, University of Rochester in Rochester, New York. Patients seen in the inpatient or outpatient setting with histologically confirmed untreated CLL will be evaluated for this study.

Patients will be treated with the following combination:

Rituximab: day 1 = 50 mg IV, then 50 mg SQ 2 x weekly for 6 cycles. Note that in the event of a first dose infusion reaction, subsequent doses may be given IV if felt necessary by the treating investigator.

Acalabrutinib: 100 mg po BID starting on day 8 of cycle 1. First dose prior to rituximab on day 8.

- Response assessments will be performed prior to the completion of cycle 12. Patients who have attained a radiographic complete response will undergo a BM biopsy to confirm CR. Patients in CR will also have MRD testing performed on peripheral blood and marrow. Patients in CR and undetectable for MRD, will stop therapy and be followed until disease progression.
- Patients not in a MRD negative CR, will continue acalabrutinib.
- Repeat response assessments will be performed at 24 cycles of therapy for those continuing on acalabrutinib. Patients in CR and undetectable for MRD, will stop therapy and be followed until disease progression, unacceptable toxicity or physician/patient discretion.

All cycles will be 28 days.

Patients will be followed until the occurrence of definitive disease progression and may discontinue therapy early for unacceptable toxicity or withdrawal from the study due to investigator decision or other reasons.

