8.7 DEFINITIVE DISEASE PROGRESSION

The occurrence of any of the following events indicates definitive PD:

- Evidence of any new disease:
 - A new node that measures $> 1.5 \text{ cm}$ in the LD and $> 1.0 \text{ cm}$ in the LPD
 - New or recurrent splenomegaly, with a minimum LVD of 14 cm
 - New or recurrent hepatomegaly, with a minimum LVD of 20 cm
 - Unequivocal reappearance of an extra-nodal lesion that had resolved
 - A new unequivocal extra-nodal lesion of any size
 - *New non-target disease (e.g., effusions, ascites, or other organ abnormalities related to CLL).

*Isolated new effusions, ascites, or other organ abnormalities are not sufficient evidence alone of PD unless histologically confirmed. Thus, a declaration of PD should not be made if this is the only manifestation of apparently new disease.

- Evidence of worsening of target lesions, spleen or liver, or non-target disease:
 - Increase from the nadir by $\geq 50\%$ from the nadir in the SPD of target lesions
 - Increase from the nadir by $\geq 50\%$ in the LD of an individual node or extra-nodal mass that now has an LD of $> 1.5 \text{ cm}$ and an LPD of $> 1.0 \text{ cm}$

- Splenic progression, defined as an increase in splenic enlargement by $\geq 50\%$ from nadir (with a minimum 2 cm increase and a minimum LVD of 14 cm)
- Hepatic progression, defined as an increase in hepatic enlargement by $\geq 50\%$ from nadir (with a minimum 2 cm increase and minimum LVD of 20 cm)
- Unequivocal increase in the size of non-target disease (e.g., effusions, ascites, or other organ abnormalities related to CLL)
- Transformation to a more aggressive histology (e.g., Richter's syndrome) as established by biopsy (with the date of the biopsy being considered the date of CLL progression if the patient has no earlier objective documentation of CLL progression).
- Decrease in platelet count or hemoglobin that is attributable to CLL.
 - The current platelet count is $<100 \times 10^9/L$ OR there has been a decrease by $>50\%$ from the highest on-study platelet count.
 - The current hemoglobin is $<100 \text{ g/L (10.0 g/dL)}$ OR there has been a decrease by $>20 \text{ g/L (2 g/dL)}$ from the highest on-study hemoglobin.

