9.6 STATISTICAL ANALYSES

The treated population is defined as all enrolled subjects who received at least 1 dose of study drug. Efficacy and safety analysis will be based on this population.

The CR rate is defined as the proportion of patients with a best overall response of complete response with or without marrow recovery. Patients who do not have a tumor response assessment for any

reason will be considered non-responders and will be included in the denominator when calculating the CR rate.

The ORR is defined as the proportion of patients with a best overall response of partial response (PR) or complete response (CR). Patients who do not have a tumor response assessment for any reason will be considered non-responders and will be included in the denominator when calculating the ORR.

Progression-free survival is defined as the time from treatment initiation until the date of first documentation of definitive disease progression or date of death from any cause, whichever occurs first. Patients who die without a reported prior progression will be considered to have progressed on the day of their death. Patients who did not progress or are lost to follow-up will be censored at the day of their last tumor response assessment. The use of a new anticancer therapy prior to the occurrence of PD will result in censoring at the date of last tumor response assessment prior to initiation of new therapy.

The safety population includes all subjects who received at least 1 dose of study treatment. Safety evaluations will be based on the incidence, intensity, and type of adverse events, as well as on clinically significant changes in the patient's physical examination, vital signs, and clinical laboratory results. Safety variables will be tabulated and presented by study drug actually received.

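### Does a late relapse seen only in the lymphocyte count need its own rule as a PFS event?

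*Combined protocol and SAP*

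**What the plan says.** Section 9.6 defines PFS as the "time from treatment initiation until the date of first documentation of definitive disease progression or date of death from any cause", whichever is earlier. It adds: "The use of a new anticancer therapy prior to the occurrence of PD will result in censoring", with the censoring date set at the last response assessment before that therapy.

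Section 8.7 opens its list with "The occurrence of any of the following events indicates definitive PD". The items cover new disease, growth of nodes, spleen, liver or non-target disease, transformation, and "Decrease in platelet count or hemoglobin that is attributable to CLL". No item concerns the lymphocyte count.

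Section 8.9 describes the early rise in lymphocytes on acalabrutinib. In that setting it describes definitive progression as "disease progression that is manifest by worsening CLL-related signs other than lymphocytosis alone". Its last sentence excepts rises caused by a treatment interruption and then says "new or increasing lymphocytosis after 6 months of starting treatment may be considered disease progression and should be confirmed as per the response criteria".

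Patients in MRD-negative CR at cycle 12 or 24 "will stop therapy and be followed until disease progression" (Section 4.1; Section 4.3 adds CRi). The same section also says: "Patients will be followed until the occurrence of definitive disease progression".

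The closing line of Section 2.3 and the opening of Section 8 make the cited iwCLL guideline the basis for response and progression. Section 8.3 has the IRC assign the response category, and Section 8.7 sends uncertain progression to it.

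**The concern.** Put the definitions in sequence and they seem to leave a hole. PFS needs definitive progression. Section 8.9 appears to take isolated lymphocytosis out of that term, then lets late lymphocytosis back in with a permissive verb and points to criteria whose written progression list has no lymphocyte test. Two assessors could classify the same patient differently and both cite the text.

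The patients who stop therapy in MRD-negative remission make this look sharper. Section 8.9 is headed as applying during therapy, and the plan does not say whether a planned stop is an interruption. If a rise in lymphocytes after stopping is not an event and new therapy begins, Section 9.6 censors the patient. Such censoring is caused by relapse, so it is informative and would flatter PFS and duration of response. It would do so in the very group in which time-limited treatment is observed.

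**Working it through.** **The plan's own figure.** Section 9.1 gives an exact 95% interval for 8 of 40 complete responses.
- Lower limit: 2.5% quantile of Beta(8, 33) = 9.05%.
- Upper limit: 97.5% quantile of Beta(9, 32) = 35.65%.
- Width: 26.60%. The largest width for n = 40 is 32.40%, at 20 of 40.

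These match the stated 9.1% to 35.6%, 26.6% and 32.4%. The criteria for complete response in Section 8.4 carry their own lymphocyte limit, so how relapse is classified does not enter this calculation. The plan gives no event count, power or target for PFS.

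**The possible readings.**
1. *Narrow.* Definitive progression always excludes lymphocytosis alone. A late lymphocyte-only relapse is then not an event, and new therapy leads to censoring. On this reading the last sentence of Section 8.9 does nothing for PFS.
2. *General rule with exception.* Isolated lymphocytosis, which Section 8.9 places mostly in the first weeks, is not progression. After six months, outside an interruption, it may be, once confirmed. Every sentence keeps a role, and a confirmed case can be an event.
3. *Guideline.* Section 8 rests progression on the iwCLL criteria, and the response criteria named in Section 8.9 can be read as pointing there. The guideline text is not in the documents, so nothing here relies on its content.

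Only reading 1 forces the favourable censoring.

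**Is there a real split between progression and definitive progression?** Section 4.1 uses both terms for follow-up. Section 9.6 moves, within one definition, from definitive disease progression to prior progression, to patients who did not progress, and to PD. That looks like loose synonyms rather than two endpoints.

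**Timing of planned stops.** Cycles last 28 days, so stops fall at about 12 × 28 = day 336 and 24 × 28 = day 672. Six months is 365.25 / 2 = 182.6 days. The stops come 336 − 182.6 = 153.4 and 672 − 182.6 = 489.4 days after that mark, so any relapse after a planned stop meets the time condition. What stays open is whether the section's heading or its interruption clause keeps these patients out. The interruption paragraph in Section 8.7 concerns temporary holds, which suggests that a planned stop is something else, although Section 8.9 does not say so.

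**Size.** One such patient is 1/40 = 2.5 points of the crude event proportion. The number is not in the documents; if it were 1, 2 or 4, the shift would be 2.5, 5 or 10 points. The expected complete responders are 0.20 × 40 = 8, and only those who are MRD negative stop. Responses first reached at cycle 24 could add to that pool if the 20% refers to one year. The crude proportion is not itself a planned statistic, so these figures only bound the scale.

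**The case for a change.** The best case for acting is that this relapse pattern is foreseeable. Section 3.1 lets progressive lymphocytosis by itself justify entry, so a patient could relapse in the same way and meet no item in Section 8.7. Footnote 6 of Table 5.1 waives the cycle 12 and 24 CT scans for patients without measurable disease at baseline, which leaves more weight on blood counts. Footnote 3 ends study collection of laboratory values after cycle 24 or on discontinuation, so a rule settled at analysis might lack data. The IRC still needs a rule to apply, and no text ranks Section 8 against the guideline.

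Part of this stands. The lack of a stated precedence is real, and so is the silence on planned stops. The data point is weaker. Footnote 3 ends routine laboratory collection, but Section 4.3 keeps patients who stop in follow-up for progression, Section 11.6 requires source support for CRF entries where appropriate, and Section 11.5 gives access to the original records. Section 9.6 cannot be applied without the start date of new therapy, so that date has to be obtained anyway. An extra laboratory entry would document a progression or new therapy that is already followed; it would not by itself decide how to classify it.

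The obvious remedy, one rule of the sponsor's choosing, names no better method. Requiring the same rule on and off drug would also be a preference, because the protocol treats lymphocytosis on a BTK inhibitor as a drug effect.

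**Conclusion.** Sections 8.7, 8.9 and 9.6 are not fully aligned, but this is a gap that the study team can fill sensibly with what the plan already provides: the timed exception in Section 8.9, the iwCLL basis in Section 8, and categorisation by the IRC. The feared bias arises only if the team adopts the one reading that gives the last sentence of Section 8.9 no part in PFS.

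The stakes are small. The endpoints are secondary, there is no comparator and no PFS test, and the primary complete response rate and its interval do not change. Each case would be worth 2.5 points of the crude event proportion in 40 patients. The number of cases is unknown, and no shift in PFS is shown.

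This conclusion assumes that the IRC works as Sections 8.3 and 8.7 describe and that local counts remain available in source records. It takes no view on which clinical criterion for progression is right.
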